### 9- Study outcomes:

- **Primary outcomes** (Most important measurable outcomes)
  - 1- Measuring changes in meibomian glands function, break up time, tear meniscus height, and lipid layer thickness in polycystic ovarian syndrome and with different drugs used in managing it.
- **Secondary outcome parameters** (other outcomes to be assessed)
  - 1- Measuring eye lid margin, conjunctival hyperemia, and ocular surface staining in polycystic ovarian syndrome and with different drugs used in managing it.
  - 2- Measuring the central corneal thickness (CCT) changes in polycystic ovarian syndrome and with different drugs used in managing it.

**10- Sample size** (number of study subjects included and justification including the clinical and statistical assumptions supporting sample size calculation)

$$\left( \frac{Z_{a/2} + Z_B}{P_1 - P_2} \right)^2 (p_1 q_1 + p_2 q_2)$$

(Takazawa & Morita, 2020)

n = sample size

Z a/2 (The critical value that divides the central 95% of the Z distribution)

ZB (The critical value that divides the central 20% of the Z distribution)

p1 = prevalence in case group

p2 = prevalence in control group.

q = 1-p

Epi Info STATCALC was used to calculate the sample size by considering the following assumptions:- 95% two-sided confidence level, with a power of 80%. &  $\alpha$  error of 10% . The final maximum sample size taken from the Epi- Info output was 26. Thus, the sample size was increased to 30 subjects with total 30 eyes in each group to assume any drop out cases during follow up.

[figure not shown]
**11- Statistical analysis** (Please describe your data analysis plan)

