Data management and analysis will performed using Statistical Package for Social Sciences (SPSS). Median and range for non-parametric measures and ordinal (scores) data. Numerical data will be presented as means  $\pm$  standard deviations (SD). Categorical data will be presented as number and percentages %. Pairwise comparisons between the two groups for normally distributed variables will be done using the Student's t-test; the Mann-Whitney test, a nonparametric test equivalent to the t-test, will be used in non-normally distributed variables. The Repeated measures ANOVA test will be used to compare the effect change within and between the study groups at different visits. The chi-square test or the Fisher's exact test will be used to compare between the groups with respect to categorical data. All p-values will be two-sided. P-values  $< 0.05$  will be considered significant

**12- Source of funding:** (Please include source of funding even if self funding)

- Faculty of Medicine, Cairo University ☐
  - Other sources: ☐
- Please specify: Self-funding

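### Section 10 gives contradictory inputs for alpha and Z_B and no values for p1 and p2, so the stated 80% power at two-sided P < 0.05 cannot be verified

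*Combined protocol and SAP*

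**What the plan says.** Section 10 prints a formula for comparing two proportions and a key to its symbols. The key reads "Z a/2 (The critical value that divides the central 95% of the Z distribution") and, in the same style, "ZB (The critical value that divides the central 20% of the Z distribution"). The two rates are named only: "p1 = prevalence in case group" and "p2 = prevalence in control group". The text gives neither a value.

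The assumptions for the Epi Info run follow: "95% two-sided confidence level, with a power of 80" per cent, and in the same list an alpha error of 10%. The result is given as: "The final maximum sample size taken from the Epi- Info output was 26". It is then raised to 30 women (30 eyes) in each group to cover dropout, with no dropout rate stated.

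Section 11 makes all p-values two-sided, and values below 0.05 "will be considered significant".

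**The concern.** Two conflicts are visible on the page. First, a 95% two-sided confidence level is an alpha of 5%, so an alpha of 10% cannot belong to the same calculation. Second, the key uses one form of words for both critical values. For the central 95% it correctly gives 1.960. For the central 20% the same convention gives 0.253, which is the value for 60% power, not 80%. The 20% is presumably meant as beta, the upper-tail area beyond 0.842, but that is not what the key says.

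This paragraph is the only justification offered for the size of the study. If either conflicting input entered the calculation, the comparison it describes has less than 80% power at the threshold used in section 11, and a non-significant difference between the drug groups would be weaker evidence than the plan suggests. With p1 and p2 absent, a reader cannot re-run the calculation to find out.

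**Working it through.** **Inputs from the plan.** Two-sided alpha 5% (95% level and formula key, section 10; threshold, section 11). Alpha 10% (section 10). Power 80% and Z_B tied to the central 20% (section 10). n = 26, raised to 30 per group (section 10). p1 and p2: no values.

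**Assumptions.** 26 is per group: it is not labelled, but it is raised to 30 in each group. The 10% alpha is two-sided, like the rest of the paragraph.

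**Critical values.**
- Two-sided 5%: Z_a/2 = 1.960. Two-sided 10%: 1.645.
- 80% power: Z_B = 0.842, the 80th percentile.
- Central 20%: the area runs from 40% to 60%, so Z = z(0.60) = 0.253, and Phi(0.253) = 0.60.

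**Can 26 be reproduced?** The formula is n = ((Z_a/2 + Z_B)/(p1 − p2))² × (p1q1 + p2q2). Without p1 and p2 it has no single answer. Assume p2 = 0.10 for illustration:
- Alpha 5%, Z_B 0.842, p1 = 0.42: (2.802/0.32)² × (0.2436 + 0.0900) = 25.6, so 26.
- Alpha 10%, Z_B 0.842, p1 = 0.38: (2.486/0.28)² × (0.2356 + 0.0900) = 25.7, so 26.
- Alpha 5%, Z_B 0.253, p1 = 0.35: (2.213/0.25)² × (0.2275 + 0.0900) = 24.9, so 25.
- Alpha 10%, Z_B 0.253, p1 = 0.31: (1.898/0.21)² × (0.2139 + 0.0900) = 24.8, so 25.

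Every reading reaches about 26 for some pair of rates, so the figure 26 does not reveal which inputs were used.

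**Power at two-sided 0.05, conditional on how 26 arose.** If 26 was obtained with a given Z_a/2 and Z_B, then L = Z_a/2 + Z_B is the standardised effect at n = 26. Power at 0.05 with n per group is Phi(L × √(n/26) − 1.960). The unknown rates cancel. The number needed for 80% power is 26 × 7.849/L², where 7.849 = (1.960 + 0.842)² before rounding.

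| Inputs assumed to have produced 26 | L | L² | Power, 26 per group | Power, 30 per group | Per group for 80% |
|---|---|---|---|---|---|
| alpha 5%, Z_B 0.842 | 2.802 | 7.849 | 80% | 85% | 26 |
| alpha 10%, Z_B 0.842 | 2.486 | 6.183 | 70% | 76% | 34 (just above 33) |
| alpha 5%, Z_B 0.253 | 2.213 | 4.899 | 60% | 66% | 42 (41.7) |
| alpha 10%, Z_B 0.253 | 1.898 | 3.603 | 48% | 53% | 57 (56.6) |

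Example, second row: Phi(2.486 − 1.960) = Phi(0.526) = 0.70. With 30, Phi(2.486 × 1.074 − 1.960) = Phi(0.711) = 0.76.

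**Dropout.** Going from 30 to 26 allows for 4/30 = 13.3% loss.

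**The case against.** The strongest reply is that both conflicts are drafting slips that never touched the calculation. Three statements agree on 5%: the 95% confidence level, the formula key and the threshold in section 11. Only the 10% phrase is out of line. No number is printed for Z_B; 0.253 is inferred from a loosely worded key, while power is stated separately ("with a power of 80" per cent) and n is credited to software output. If Epi Info was run at 95% and 80%, 26 per group gives 80% power by construction, and 85% if all 30 complete.

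This stands, and it limits the point. A reader might infer from the contradictions that 80% power fails at P < 0.05. The documents do not support that: it would require that the 10% alpha or the literal Z_B was actually used, and nothing shows this.

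A second reply also stands. The formula compares two proportions, whereas the primary outcomes in section 9 are changes in gland function and tear-film measures, and section 11 plans t-tests, Mann-Whitney tests and repeated measures ANOVA for numerical data. The percentages above are therefore not the power of those analyses.

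What the slip argument does not do is restore the 80%. The 10% appears in the list of assumptions for the software run, and without p1 and p2 nobody can confirm which inputs were entered. A figure after the paragraph is not reproduced in the text available. If it shows the software's inputs, they belong in the text.

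**Conclusion.** The paragraph is wrong as written: it states two incompatible alphas and describes Z_B in a way that does not match 80% power. Because p1 and p2 are also missing, 26 can be neither reproduced nor refuted, and 80% power at two-sided 0.05 cannot be verified. Across the four readings, power with 26 per group runs from 48% to 80%, and with 30 per group from 53% to 85%. The three unfavourable readings stay below 80% even with no dropout. The favourable reading is the one most of the plan's own statements agree with, so the point is a failure of justification, not a demonstrated loss of power. The figures rest on 26 being per group, on a two-sided 10% alpha, and on the normal approximation in the printed formula.

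**What to change.** In section 10:

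1. Delete the 10% alpha and state one two-sided alpha of 5%, matching section 11.
2. Define Z_B as 0.842, the 80th percentile of the standard normal distribution.
3. State the values of p1 and p2 and the assumed dropout rate. Without the two rates no power can be restated.
4. Re-run the calculation with all inputs shown. Keep 30 per group and report the power that 26 evaluable women per group give at two-sided 0.05.

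The cost is wording and one re-run, with no additional patients. The stated power may become less favourable; if so, the plan should say so before the results are interpreted.

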#### 5. Background and Rationale: (Describe the research question and justification for undertaking the study explaining the aspects of novelty in the study)

Polycystic ovary syndrome (PCOS) is one of the most common endocrinopathies, affecting approximately 9% to 18% of women in reproductive age. Although the exact pathogenesis of PCOS remains unclear, the characteristic symptoms include oligoanovulation, polycystic ovarian morphology could be explained by hyperandrogenism and hyperestrogenemic not balanced by progesterone. The endocrine, inflammatory, and metabolic changes associated with PCOS have consequences for vision, including neurovascular, metabolic changes in the retina, macular and optic nerve thickness changes.

In recent years it has been discovered that female sex steroids have both systemic and ocular effects, Estrogen, progesterone and androgen receptors have been found in the cornea, lens, iris, ciliary body, retina, lacrimal glands, meibomian glands and conjunctiva, The influence of hormone replacement therapy in menopausal women remains unclear, as some authors support the idea that it improves the quality and the volume of the tear film, whereas others have shown that it increases the risk of dry eye, It's possible that HRT may alleviate postmenopausal dry-eye symptoms by increasing goblet cell density. However, other studies suggest that HRT worsens dry-eye symptoms in some cases, and estrogen-only HRT seems to be worse than a combined estrogen and progesterone therapy.

Reports are stressing on the effect of PCOS on tear film stability rather than amount of the tears denoting the possible effect on meibomian glands (MGs) functions, Loss and morphological deterioration of the MGs are observed in PCOS patients, Yonca Asfuroglu et al. reported that Dry eye was well established in patients with PCOS. They proposed that hyperandrogenism, insulin resistance and subclinical inflammation may be possible contributing factors to the Dry eye spectrum in these patients, They correlated the severity of the Dry eye with the level of inflammation and hyperandrogenism.

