*For Treatment of Non-fertility outcomes*, combined oral contraceptive pills (COCs), metformin and anti-androgen drugs are used. COCs are recommended as first-line medical treatment for the management of hyperandrogenism and regulation of menstrual cycles, A study by Chen et al. reported that COCs have no direct

impact on Dry eye, They found no significant differences in Dry eye, as measured by tear osmolarity and ocular surface disease index (OSDI) or Symptom Assessment in Dry Eye (SANDE) questionnaires, between patients taking OCPs and those not taking OCPs. However, results were not conclusive.

Because of the metabolic features of PCOS such as insulin resistance and hyperinsulinemia; insulin-sensitizing agents, especially metformin, have been used as a treatment option for PCOS with OCPS as the second line of treatment. Metformin has a protective effect in diabetic retinopathy, glaucoma, and age related macular degenerations, It can also improves objective measures of Dry Eyes and focus score in Sjögren's Disease.

[figure not shown]
The role of antiandrogens in the treatment of hirsutism in PCOS is controversial; however, there is some weak evidence that flutamide and spironolactone reduce hirsutism. Ilaria Macche et al. found that ocular surface findings are improved by systemic anti-androgen treatment in PCOS and correlate with the severity of the androgen excess-related skin signs.

*For Treatment of Fertility Indications,* Pharmacological options include ovulation induction with clomiphene citrate (CC), letrozole (aromatase inhibitor), metformin, and gonadotrophins; The effect of clomiphene citrate (ovarian stimulant) on vision is minimal; reduction in foveal flicker sensitivity was the only observed visual disturbance.

Although visual disturbance is a possible side effect of aromatase inhibitors use, its incidence is quite variable. Studies found increased tear osmolarity and meibomian gland drop out in women on letrozole with symptomatic dry eye.

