## **6. Objectives:** (describe specific objectives or hypotheses behind the study)

The purpose of this study is to prospectively evaluate the ocular surface effects of polycystic ovarian syndrome and different drugs used in its management.

**7. Study Design:** (Please fill in the appropriate study design, see attached PDF guide)

- Descriptive: - Survey (cross sectional)

☐  
☐

- Qualitative

- Analytic: - Observational: - Case-control study

- Cross sectional analytic study

- Cohort (Longitudinal) study

☐  
☐  
☒

- Experimental: - Randomized Clinical Trial

Phase: ☐

- Non-randomized clinical trial

- Animal study

- Cellular study

☐  
☐  
☐

- Others: Please describe:

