**8. Study Methods**

- **Population of study:** (Please provide all details regarding participants including gender, age range and disease conditions. Also indicate if this protocol involves children, prisoners, pregnant women or cognitively impaired or mentally disabled subjects)

Two groups with confirmed laboratory and ultrasonography diagnosis of PCOS , First group will include 30 eyes of 30 females in childbearing period (18-40 years old) scheduled for treatment for non- fertility indications with oral contraceptive pills (as a first line of treatment), and the second group will include 30 eyes of 30 females in childbearing period (18-40 years old) scheduled for treatment with Clomiphene citrate (as a first line of treatment), for fertility indications.

- **Study location:** (Please provide where the study will be conducted and from where study participants will be recruited)

Patients will be recruited from gynecology and dermatology Kasr Al-Ainy clinics and will undergo their ophthalmic examination and investigations at the department of ophthalmology, Kasr Al-Ainy school of medicine.

- **Inclusion criteria:**

1. Females at child bearing period (18-40 years old).
2. Patients recently diagnosed with polycystic ovarian syndrome.

- **Exclusion criteria:**

1. Patients who were diagnosed with Dry eye disease.
2. Patients who were treated with hormonal replacement therapy, Metformin, Aromatase inhibitors, clomiphene citrate or androgen antagonists.
3. Patients who underwent ocular surgeries.
4. Patients with history of diabetes mellitus or hypertension.

- **Methodology in details:**

Two groups with confirmed laboratory and ultrasonography diagnosis of PCOS, First group will include 30 eyes of 30 females in childbearing period (18-40 years old) scheduled for treatment for non- fertility indications with Estradiol valerate / Norgestre tablets for six months, The second group will include 30 eyes of 30 females in childbearing period (18-40 years old) scheduled for treatment with Clomiphene citrate for fertility indications for 6 months.

- Follicle stimulating hormone (FSH), luteinizing hormone (LH) , androgen, estrogen, progesterone , fasting insulin and neutrophil to lymphocyte ratio (NLR) will be obtained.
- The two groups will undergo complete ophthalmic examination including :

\*Full history.

\*Standard Patient Evaluation of Eye Dryness Questionnaire (SPEED) in order to quickly track the progression of dry eye symptoms over time.

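### Drug is fixed by indication in a non-randomised cohort, but no between-group test in section 11 is adjusted and no contrast is named as decisive, so drug effects cannot be separated from differences between the women

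*Combined protocol and SAP*

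**What the plan says.** - **Design.** Section 7 marks the study as observational, "Cohort (Longitudinal) study". No randomisation, matching or stratification is described.
- **Groups (section 8).** One group is "scheduled for treatment for non- fertility indications with oral contraceptive pills (as a first line of treatment"; the other is "scheduled for treatment with Clomiphene citrate (as a first line of treatment), for fertility indications". Thirty women are planned in each, recruited from gynaecology and dermatology clinics, with nothing said about balancing the groups.
- **Rationale (section 5).** "COCs are recommended as first-line medical treatment for the management of hyperandrogenism and regulation of menstrual cycles". Androgen excess, insulin resistance and low-grade inflammation are put forward as possible contributors to dry eye in PCOS. Of one cited study the protocol says: "They correlated the severity of the Dry eye with the level of inflammation and hyperandrogenism".
- **Data (section 8).** Sex hormones including androgen are measured, and "fasting insulin and neutrophil to lymphocyte ratio (NLR) will be obtained". Eye examination and laboratory tests take place before treatment, at 3 months and at the end of the course.
- **Outcomes (section 9).** The primary outcomes are changes in gland function, break-up time, tear meniscus height and lipid layer, in PCOS and under the different drugs.
- **Analysis (section 11).** "Pairwise comparisons between the two groups for normally distributed variables will be done" by t-test, with Mann-Whitney for non-normal variables and chi-square or Fisher for categories. A repeated measures ANOVA is to compare change within and between groups across visits. All tests are two-sided at 0.05. No covariate is named, no test is called primary, and nothing limits how a group difference may be read.

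**The concern.** Every woman on clomiphene has a fertility indication and every woman on pills does not. Any difference between the two kinds of patient is therefore carried by the drug label. The protocol itself gives reason to think that such differences could matter: it links pills to the management of androgen excess, and it links androgen excess, insulin resistance and inflammation to dry eye. It measures all three before treatment but gives them no role as covariates.

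Two gaps follow. First, several unadjusted between-group tests are available at 0.05. Some compare levels rather than change, and the plan does not say which one decides. Second, even the comparison of change is unadjusted, so a baseline factor that influences the six-month course can pass for a drug effect. The contrast between drugs is a main use of these data, and a positive result could not be interpreted.

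**Working it through.** **Inputs.** From the documents: 26 women per group (the calculated size in section 10, raised to 30 for dropout; 26/30 means a 13.3% loss), three visits, two-sided 0.05. The 26 cannot be reproduced because the two prevalences are not stated; it serves here only as the evaluable number. Assumed: no drug effect, the size of the group difference, and the correlation ρ between visits (0.5 to 0.7).

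**1. t-test on levels at a follow-up visit.** If the groups differ by b SD for reasons other than the drug, the test statistic is noncentral t with df = 2n − 2 and noncentrality δ = b·√(n/2). For n = 26, df = 50, the critical value is 2.009 and √(26/2) = 3.606.

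| b (SD) | δ | False rejection |
|---|---|---|
| 0 | 0 | 5.0% |
| 0.1 | 0.361 | 6.4% |
| 0.2 | 0.721 | 10.9% |
| 0.3 | 1.082 | 18.6% |
| 0.5 | 1.803 | 42.4% |

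With all 30 per group retained, 0.5 SD gives 47.8%.

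**2. ANOVA group main effect.** This compares means over the three visits, whose SD is √((1 + 2ρ)/3). A stable 0.5 SD shift becomes 0.5 divided by that SD.

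| ρ | SD of mean | Shift | δ | False rejection |
|---|---|---|---|---|
| 0.5 | 0.816 | 0.612 | 2.208 | 58% |
| 0.6 | 0.856 | 0.584 | 2.105 | 54% |
| 0.7 | 0.894 | 0.559 | 2.016 | 51% |

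**3. ANOVA group-by-visit interaction, or change from baseline.** A shift that is equal at every visit cancels: (follow-up + b) − (baseline + b) = follow-up − baseline. Simulation of the same setting (5,000 trials each) gives 5.3%, 4.6% and 5.2% for ρ = 0.5, 0.6 and 0.7.

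**4. ANCOVA on the baseline outcome.** With a stable shift, the adjusted difference is b(1 − ρ) = 0.25, 0.20 and 0.15 SD, not zero. Simulated rejection is 16%, 14% and 11%.

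**5. Confounding of change.** Let a baseline covariate differ by D SD between groups and correlate r with change within groups. The spurious difference in change is b = r·D SD of change, and the formula in step 1 applies.

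| D | r | b = r·D | Unadjusted | Adjusted for the covariate (simulated) |
|---|---|---|---|---|
| 0.5 | 0.3 | 0.15 | 8.3% | 5% |
| 0.5 | 0.5 | 0.25 | 14.3% | 5% |
| 1.0 | 0.3 | 0.30 | 18.6% | 5% |
| 1.0 | 0.5 | 0.50 | 42.4% | 5% |

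A separate simulation of this range gave 8–44% unadjusted and 5–7% adjusted. The interaction in step 3 gives no protection here, because the groups really do change differently, though not because of the drug.

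**6. Price of adjustment.** A covariate that differs by D inflates the variance of the group effect by 1 + D²/4; if it explains a share R² of the outcome, the variance is multiplied by 1 − R². Take 30 per group and 80% power at 0.723 SD (1.960 + 0.842 = 2.802). With D = 1 and R² = 0, the variance factor is 1.25, 2.802/√1.25 = 2.506, and power = Φ(2.506 − 1.960) = about 71%. With D = 0 and R² = 0.25, power is about 90%.

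**The case against.** The best defence is that the plan already compares change. A pre-treatment visit is scheduled, the primary outcomes are defined as changes, and the ANOVA is described as comparing change within and between groups. Its natural reading is the interaction, which holds 5% under a stable difference. This stands, and it would be wrong to say that the plan relies only on raw t-tests. But section 11 does not name the interaction or make it decisive, and step 5 shows that it does not deal with confounders of change.

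Several stronger readings are tempting, and the documents do not support them:
- *That the pill group will have higher androgen, insulin or NLR.* Section 5 recommends pills for cycle regulation as well as androgen excess, section 8 says only non-fertility indications, and both groups have confirmed PCOS. Imbalance is plausible, not documented. The link to dry eye is stated only as possible.
- *That the laboratory values go unused.* They are repeated at each visit and can be compared like any other variable. What is missing is a covariate role.
- *That t-tests at months 3 and 6 are the planned drug comparison.* Section 11 ties the t-test to no visit; it may include baseline. The 42% applies only if a follow-up t-test is used for inference.
- *That group differences will be reported as drug effects.* The objective is to evaluate, and no comparative hypothesis is stated. The supportable statement is that the two cannot be separated.

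The exclusions (diagnosed dry eye, diabetes, hypertension, listed prior treatments) narrow the population, but they do not balance age, androgen, insulin or inflammation between the groups.

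**Conclusion.** The point holds, as a should-fix. It is certain from the text that drug and indication coincide, that no between-group test is adjusted, and that no contrast is named as decisive. The size is conditional. Under a stable 0.5 SD difference, false rejection is about 42% for a follow-up t-test, about 51–58% for the ANOVA main effect and about 5% for the interaction. Under covariate imbalances of 0.5–1.0 SD with correlations of 0.3–0.5 with change, an unadjusted change comparison rejects falsely in about 8% to 42–44% of trials. The documents supply no SDs or group differences, so every one of these inputs is an assumption, and with no imbalance there is no bias.

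A reader might also infer that adjustment would yield a clean drug effect. It would not: it deals with measured factors only, and since indication and drug coincide, residual confounding remains.

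**What to change.** In section 11:

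1. Name the between-group difference in change from baseline (the group-by-visit contrast) as the deciding comparison. Estimate it by regressing change on group, age, and baseline androgen, fasting insulin and NLR. Use only pre-treatment laboratory values as covariates, because later values may themselves reflect treatment.
2. Label as descriptive the ANOVA group main effect and any t-test, Mann-Whitney, chi-square or Fisher comparison at follow-up visits.
3. If ANCOVA on the baseline outcome is added as a sensitivity analysis, state that it does not fully remove a stable group difference (11–16% rejection in step 4).
4. Word conclusions as adjusted associations, and state that confounding by indication cannot be excluded.

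Cost: SAP wording and one regression in SPSS on data already planned, with no new visits, tests or participants. It uses about four degrees of freedom out of 52–60 women. Some precision is lost if the covariates differ between groups: for one covariate, at worst in the cases examined, power falls from 80% to about 71% (a 1 SD imbalance in a covariate that explains no outcome variance). A balanced covariate that explains 25% of the variance would raise it to about 90%.

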\*Manifest refraction.

\* Corrected distance visual acuity.

\* Anterior segment examination using slit lamp, Schirmer's test and tear film breakup time test.

\* Fundus examination.

\* Measuring central corneal thickness (CCT) using Corneal pachymetry.

•Beside Schirmer's test, tear film breakup time test and fluorescein break-up patterns, Dry eye assessment will be performed using Dry Eye Diagnostic System device (D130, Medi-Works Precision Instruments; Shanghai, China). Device to have a Dry eye diagnosis brings out an automatic result of non-invasive break up test (NIBUT) and tear meniscus height after taking one video. It is a fully automatic analysis system to provide efficient quantified evaluation for the overall stability of the tear film. Also it uses identification system that depicts the tear meniscus area and measures the tear height automatically.

The device also automatically analyses the meibomian glands, lipid layer thickness, and eyelid margin. The built-in infrared lighting system helps to obtain the enormous image scope of the meibomian glands. Finally the device identifies and calculates percentages of

conjunctival congestion and ciliary congestion, Thus evaluating the severity of eye congestion. If the degree of severity of eye congestion is more than two, it is abnormal.  
\*Examination and laboratory tests will be done before, 3 months after starting treatment and after finishing the treatment course.

- **Intervention:**

☒ Diagnostic intervention (please describe):

Imaging ocular surface using dry eye diagnostic system.

☐ Therapeutic intervention (please describe):

☐ No intervention

- **Does the research involve?**

☒ Human participants

☐ Biological samples/Tissues

☐ Identifiable private data/Information

- **Type of consent of study participants:**

☒ Written consent

[figure not shown]
☐ Oral consent

☐ No consent needed (Please justify)

- **Potential risks:**

(Please mention all risks involved even mild ones as pain, discomfort, chance of infection or psychological effects)

1- No possible risks

- **Confidentiality of data:** (Please explain how privacy and confidentiality of data and records will be maintained)
- Names and private data of patients will not be published, only the results of the study will be analyzed and published.

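### Section 11 names an equal-variance t-test and a three-visit ANOVA without a sphericity correction; Welch's test and Greenhouse-Geisser P values would be safer at almost no cost (minor)

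*Combined protocol and SAP*

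**What the plan says.** Section 11 (Statistical analysis) sets the between-group test: "Pairwise comparisons between the two groups for normally distributed variables will be done using the Student's t-test". Mann-Whitney "will be used in non-normally distributed variables". For the longitudinal data, "The Repeated measures ANOVA test will be used to compare the effect change within and between the study groups at different visits". On the threshold, "All p-values will be two-sided", and values below 0.05 "will be considered significant". The section names no unequal-variance version of the t-test, no variance check, and no sphericity check or correction.

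Section 8 (Study Methods) plans 30 women in each group, one eye each. One group takes oral contraceptive pills for non-fertility indications. The other is "scheduled for treatment with Clomiphene citrate for fertility indications for 6 months". There are three assessments: "Examination and laboratory tests will be done before, 3 months after starting treatment and after finishing the treatment course". Section 10 (Sample size) raises 26 to 30 in each group "to assume any drop out cases during follow up". It states no loss rate and no expected difference in loss between the groups.

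**The concern.** Student's t-test pools the two group variances. That is harmless when the group sizes are equal or the variances are equal. When neither holds, the pooled standard error is wrong: too small if the smaller group has the larger SD, too large if it has the smaller SD. Here women enter a group by treatment indication and take different drugs, so nothing in the design makes the spread equal. Some loss is expected and need not be balanced.

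The ANOVA has a second, separate weakness. Its visit and group-by-visit F tests assume sphericity, meaning equal variances of the differences between pairs of visits. A violation raises the error rate even when nobody is lost.

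At stake is whether the 0.05 threshold is the real false-positive rate for the between-drug comparison, whether confidence intervals have their stated coverage, and whether power is lost when the error moves the other way. SPSS prints both versions of each result, so silence also leaves the choice of P value open until after the data are seen.

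**Working it through.** **Inputs from the documents.** Two-sided 0.05 and the named tests (section 11); 30 per group and three visits (section 8); 26 raised to 30 (section 10).

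**Inputs assumed.** SD ratios, visit correlations and unequal completing numbers, because the documents give none. Data are simulated as normal with no true effect.

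**The plan's own figure.** The 26 cannot be recomputed, because section 10 gives no values for the two prevalences. The inflation can: 4/30 = 13.3%, and 26/(1 - 0.133) = 30. Two patterns stay close to this allowance: 30 v 26 (all of one group's allowance lost, none of the other's) and 28 v 24 (52 women in total, which is 2 x 26).

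**Why the pooled standard error goes wrong.** The test uses s_p²(1/n1 + 1/n2), with s_p² = [(n1-1)σ1² + (n2-1)σ2²]/(n1+n2-2). The true variance of the difference is σ1²/n1 + σ2²/n2. Take SDs of 1 and 2, with the larger SD in group 2:

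- 30 v 30: s_p² = (29 + 116)/58 = 2.5. The test uses 2.5 x 0.0667 = 0.167; the truth is 0.033 + 0.133 = 0.167. No distortion.
- 30 v 26: s_p² = (29 + 100)/54 = 2.389. The test uses 2.389 x 0.0718 = 0.1715; the truth is 0.0333 + 0.1538 = 0.1872. The standard error is √(0.1715/0.1872) = 0.957 of what it should be.
- 30 v 20: s_p² = (29 + 76)/48 = 2.1875. The test uses 0.1823; the truth is 0.2333. The ratio is 0.884.

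**Simulated error of Student's t at nominal 5%** (400,000 replicates per row; Monte Carlo standard error √(0.05 x 0.95/400,000) = 0.03 percentage points):

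| Completing | SD ratio | Larger SD in smaller group | Larger SD in larger group |
|---|---|---|---|
| 30 v 30 | 1.5 to 3 | 5.0-5.3% (equal sizes) | 5.0-5.3% (equal sizes) |
| 30 v 26 | 1.5 | 5.7% | 4.4% |
| 30 v 26 | 2 | 6.3% | 4.3% |
| 28 v 24 | 1.5 | 5.8% | 4.4% |
| 28 v 24 | 2 | 6.3% | 4.2% |
| 30 v 22 | 2 | 7.6% | 3.3% |
| 30 v 20 | 1.5 | 7.0% | 3.5% |
| 30 v 20 | 2 | 8.5% | 2.8% |

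Repeat runs of the 30 v 26 and 28 v 24 cells gave 5.7-6.4% and 4.2-4.5%. A loss as heavy as 28 v 16 gives 7.8% at ratio 1.5 and about 10% at ratio 2. With equal SDs, every combination of sizes gives 4.9-5.1%. Welch's test gives 4.9-5.2% throughout.

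**ANOVA visit and group-by-visit tests, uncorrected.** Epsilon is 1 under sphericity and at least 1/(3-1) = 0.5 for three visits.

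- Non-sphericity alone, no losses: about 5.5-6.5% at epsilon 0.74-0.84, and 7.9-8.5% near 0.53. Greenhouse-Geisser returns this to about 4.5-5.2%.
- Unequal group SDs as well (ratio 1.5 to 2, epsilon 0.78-1.0) at 30 v 26: 5.9-7.5%, or 3.8-5.4% in the other direction.
- Greenhouse-Geisser does not remove the part due to unequal variances. At SD ratio 1.5 it leaves about 6.4-7.1% at 28 v 20 and 7.8-8.6% at 28 v 16. At 30 v 20 with ratio 2 it leaves 8.5-9.3%.
- Welch's test on change scores gives 4.7-5.3%, including at unequal sizes and SDs.

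**The case against.** The plan is 30 v 30 with the same allowance in both groups, and at equal sizes the t-test is within 0.3 points of nominal even at an SD ratio of 3. That stands, and it keeps the point minor.

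Three stronger readings are tempting, and the documents support none of them.

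- **The true error rate is 7-10%.** For the t-test this needs one group to lose about a third or more (10/30 = 33% for 20 completers, 14/30 = 47% for 16) with clearly unequal SDs. At ratio 2 a loss of 8/30 = 27% already gives 7.6%. No such loss or SD is stated anywhere.
- **Losses will probably be unequal because one group is trying to conceive.** This is inference. No section says that women who conceive leave follow-up, and the last assessment is tied to finishing treatment, so stopping early does not by itself remove it. Unequal losses with equal SDs also do no harm.
- **The plan rejects a correction.** It is silent; it neither adopts nor excludes one.

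It can also be said that, if one group did lose a third of its women, bias from informative loss in a non-randomised comparison would matter more than a few points of type I error. That is fair, and Welch's test does not address it. It does not argue for keeping the pooled test.

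**Conclusion.** The point holds as a minor, free improvement. The named t-test depends on equal variances once group sizes differ, and the design does not assure equal variances. At the plan's own loss allowance, and assuming an SD ratio of 1.5 to 2, the error at nominal 5% is about 5.7-6.4%, or 4.2-4.5% if the larger group has the larger SD. The 7-10% and 2-4% ranges belong only to heavy one-sided loss combined with clearly unequal SDs. The sphericity issue needs no losses: about 5.5-6.5% at moderate epsilon and about 8% near the minimum. All these sizes depend on assumed SDs, correlations and completing numbers, since the documents supply none.

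**What to change.** In section 11, before any data are seen:

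1. Replace Student's t-test with Welch's t-test (the SPSS row 'equal variances not assumed') for normally distributed variables, and report its mean difference with the 95% confidence interval. Leave Mann-Whitney in place for non-normal variables.
2. State that, for normally distributed measures, the between-drug comparison of change is Welch's test on the change from baseline to follow-up.
3. State that Greenhouse-Geisser P values are reported for the visit and group-by-visit ANOVA tests, and note that this correction does not deal with unequal group variances at unequal numbers. That is why item 2 is needed.

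The cost is a few sentences and no new data. SPSS already prints these results. With equal SDs, power is 80.0% for Welch against 80.05% for Student's t at 30 v 30, and 80.1% against 80.35% at 28 v 20. Where the larger group has the larger SD, Welch gains power: 80% against 76% at 28 v 20 with SD ratio 1.5.
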